patients must be in New York Heart Association (NYHA) class II, III, or IV with a left ventricular ejection fraction (LVEF) of ≤40%. The inclusion and exclusion criteria are shown in Table 1. A total of 165 patients will be included over 6 month. In total, 11 hospitals (local investigators) in Belgium with an HF clinic employing at least one certified HF nurse will be participating in patient recruitment. Patients are not randomised and will all be participating in the smartphone digital support intervention.

A screening register will be kept including reasons why eligible patients that do not participate are disregarding inclusion. Patients refusing participation will also be asked to complete a quality of life (QOL)-questionnaire at 6 months and 12 months which will be answered online. A total of 165 patients (who do not want to participate) will be asked to answer this questionnaire.

So the app will be made available to 165 patients for home monitoring and another group of 165 patients without an application will be asked to answer quality of life questionnaires.

Patients who agree to use the application can continue to use it after the study, if they wish.

Inclusion criteria	Exclusion criteria
Diagnosed with HF – NYHA class II-IV	Acute coronary syndrome
LVEF ≤40%.	High urgent listed for heart transplantation
Hospitalisation due to decompensated HF at the moment of inclusion or up to 1 week prior to inclusion (i.e. discharged ≤1 week prior to inclusion).	Planned revascularisation, TAVI, MitraClip and/or CRT implantation within 3 months after inclusion
Owning a smartphone and able to use an application	Known alcohol or drug abuse
Written informed consent obtained	Terminal renal insufficiency with haemodialysis or peritoneal dialysis
	Impairment or unwillingness to use the digital support equipment (e.g. dementia, impaired self-determination, lacking ability to communicate)
	Existence of any non-cardiac disease reducing life expectancy to less than 1 year
	Age <18 years
	Participation in other treatment studies or remote patient management programmes

Table 1 – Inclusion and exclusion criteria. NYHA: New York Heart Association. LVEF: left ventricular ejection fraction. CRT: cardiac resynchronisation therapy. TAVI: transcatheter aortic valve implantation.

Digital support platform

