The digital support intervention uses the Comunicare patient support solution (Figure 1) specifically designed for digital support of HF. The solution consists of a smartphone-based mobile application designed to be used by patients and a web-based dashboard application to be used by the caregivers. The application is a class 1 certified medical device. It includes

different modules for patient education, medication adherence, tracking of vital signs and symptoms, electronic patient-reported outcome (ePRO), appointments, and video consultation.

Patient Education module: a knowledge base has been configured into the application to provide patients with information about HF based on the latest ESC guidelines (1) and the local reimbursement context. The patient information that is provided includes descriptions of the function of the heart, the causes of HF, and advice about how to self-manage and understand HF.

[figure not shown]
[figure not shown]
Medication adherence: the application enables patients to maintain a medication list and to configure a reminder system to receive notifications. If medication is not taken an explanation for non-intake can be provided.

Tracking of vital signs and symptoms: the application enables patients to track and input vital signs and symptoms as recommended by the caregivers. A notification can be configured to remind the moment of measurement. Measured values can be inserted manually or captured directly from validated connected devices (blood pressure monitor, weight scale, activity tracker). Alarm limits can be set, and an alarm will then be triggered as soon as an input breaches the alarm limit. A Bluetooth-compatible blood pressure monitor and weighing scale will be provided at inclusion. If preferred by the patient manual input through their own devices can be performed.

Electronic patient-reported outcome (ePRO): the application enables patients to complete questionnaires about their QOL. A notification can be configured to remind the moment to fill the questionnaires. When available, scoring of the questionnaires is generated in the dashboard for caregivers.

Appointments and video consultation: the application includes an electronic agenda that can be input manually by the patients or automatically synchronized with the hospital system. It also includes a secure video consultation that can be triggered by the caregivers when deemed necessary after reviewing the patient-reported data.

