At inclusion, an account on the smartphone application will be created for the patient and the application will be installed on the patient's smartphone. Instructions on how to use the application will be provided. Patients will be included for 6 months in which they will be asked to use the different modalities of the smartphone application. There will be low-threshold contact with a study nurse if the patient doesn't use or doesn't know how to use the application, as well as when predefined alarm limits are crossed. In case of patients that are

very motivated to participate in the intervention but do not own a smartphone, a smartphone can be provided by the study sponsor for the duration of the study. No costs will be charged to the patient, also in case of loss or damage

Personalised alarm limits that can be predefined include:

- Heart rate: an upper rate will be set to detect possible atrial fibrillation
- Weight gain: ideal weight and alarm weight can be set by the case nurse.
- Blood pressure: hypotension (under normal limits for the specific patient) and extreme hypertension.
- Not using the application, no measurement input by the patient for a predefined time.

After 6 months the inclusion will be ended. If the patient and the care providers deems it necessary for the continuity of care, they may continue using the application after the 6 months period of the study. A new informed consent document should be signed and the application, inside or outside the study, will remain the same. Only the data collected during the 6-month period of the study will be used for the initial data analysis. Further data analysis of the additional data after 6 months may take place in a second stage. 6 months after the end of the study, during a routine appointment (standard of care) of the patient with his cardiologist, he will be asked to answer questions about his well-being again.

Data collection during the trial

Data that will be collected by the smartphone application and the caregiver application for analysis purposes throughout the trial includes parameter measurement (blood pressure, heart rate, weight), medication adherence by using the medication module, and patient-reported outcome questionnaires. In the caregiver dashboard application information on time spent on the caregiver dashboard application and all input (time spent, change in therapy, contacts) by caregivers (nurses, cardiologists, others) will be collected.

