Table 2 – intervention design. ECG: electrocardiogram. ePRO: electronic patient-reported outcome. NT-proBNP: N-terminal prohormone of brain natriuretic peptide. KCCQ-12: Kansas City Cardiomyopathy Questionnaire. EQ5D: EuroQol 5-dimension questionnaire. HeartQoL: Health-related quality of life questionnaire. PHQ9: patient health questionnaire-9. HLS-EU-Q16: European Health Literacy Survey Questionnaire. EHFSB-9: European Heart Failure Self-care Behaviour scale revised into a nine-item scale. SUTAQ: Service User Technology Acceptability Questionnaire. WPAI : work productivity and impairment.

Health economic analysis

The costs considered for the cost-effectiveness analysis are direct costs of the smartphone-based digital support intervention and the care utilisation recorded during the inclusion of the trial. The costs for the digital support intervention consist of costs for data management using the application, costs for devices that are provided in selected patients (blood pressure monitor, weighing scale), and personnel costs for inclusion and time spent on follow-up of alarms.

Information on care utilisation will be collected at the end of the trial. Former studies have demonstrated that hospitalisation costs are the key driver of HF-related costs (7,8). This study will thus focus on reduction in length of hospital stay and reduction in rehospitalisations after initial hospitalisation. The 30-day and 90-day rehospitalisation rates will be assessed. All hospital-related costs will be collected from the hospital billing and financial departments. A distinction will be made between scheduled and non-scheduled hospitalisations. Scheduled hospitalisations for elective procedures and scheduled visits with the cardiologist or general practitioner will not be included in the cost-evaluation.

Implementation cost and cost-effectiveness will be assessed in this trial following a pre-post economic model. A historical cohort of all patients hospitalised for HF on a cardiology ward in 2019 in all participating centres will be assessed for comparison. Hospital bills and hospital administrative data based on the international classification of disease (ICD)-codes will be collected. Propensity matching will be applied.

QOL and healthcare-related costs will be collected in selected patients refusing to participate in the smartphone intervention.

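### The intervention cost list reads as complete but has no line for sponsor-supplied smartphones or for caregiver time outside inclusion and alarms

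*Protocol*

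**What the plan says.** Under Health economic analysis, the direct cost of the intervention is introduced with "The costs for the digital support intervention consist of costs for data management using the application". It continues with "costs for devices that are provided in selected patients (blood pressure monitor, weighing scale" and ends with "personnel costs for inclusion and time spent on follow-up of alarms". Nothing marks the list as a set of examples. Care utilisation during the trial is a second cost component, with hospital costs taken from the billing and financial departments. Elective admissions and scheduled visits to the cardiologist or general practitioner are left out.

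The intervention itself is described in three other places:

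- Digital support platform: "A Bluetooth-compatible blood pressure monitor and weighing scale will be provided at inclusion", followed by "If preferred by the patient manual input through their own devices can be performed". The same section lets caregivers start a video consultation at their discretion after reviewing what the patient has reported.
- Smartphone intervention: for motivated patients without a phone, "a smartphone can be provided by the study sponsor for the duration of the study", and "No costs will be charged to the patient, also in case of loss or damage". Table 1, however, lists "Owning a smartphone and able to use an application" as an inclusion criterion.
- Data collection during the trial: time on the caregiver dashboard is recorded, as is all caregiver input, including contacts.

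**The concern.** Implementation cost and cost-effectiveness are stated objectives, and the Discussion offers the results for reimbursement decisions in Belgium. The ICER numerator is the intervention group's mean cost minus the historical cohort's. An intervention input that is used but not priced makes the app look cheaper than it was. Nothing offsets this, since neither the 2019 cohort nor the patients who refuse participation have that input. The protocol measures caregiver time in full, but its costing rule prices only the part spent on inclusion and alarms. Equipment is limited to two named devices, while a third may be supplied.

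**Working it through.** The protocol states no intervention cost, unit price, number of phones or number of consultations, so there is no figure to reproduce. The check sets each input against the cost list.

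| Input | Where described | Line in the cost list? |
|---|---|---|
| Blood pressure monitor and scale | Digital support platform | Yes, wherever provided |
| Account creation, installation, instruction | Smartphone intervention (at inclusion) | Yes, personnel for inclusion |
| Contact after the non-use alarm | Smartphone intervention (non-use is among the alarm limits) | Yes, alarm follow-up |
| Video consultation after an alarm | Digital support platform | Yes, alarm follow-up |
| Smartphone lent, or replaced after loss or damage | Smartphone intervention | No |
| Dashboard review with no alarm | Digital support platform; logged under Data collection | No |
| Video consultation after data review, no alarm | Digital support platform | No |

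Three rows have no line. Write the omitted cost per patient as

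o = s × p + h × r,

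where s is the share of patients lent a phone, p the cost per phone, h the uncosted caregiver hours per patient and r the hourly rate. All four are zero or positive, so o ≥ 0. The true cost difference is the stated difference plus o, because the comparators contribute nothing to o. This fixes the direction but not the size.

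The following figures show only the order of magnitude. Every input except the 165 patients is an assumption, not taken from the protocol.

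- Smartphones: s from 0 to 20%, p from EUR 100 to 400. Low end: 0 × 100 = EUR 0. High end: 0.20 × 400 = EUR 80 per enrolled patient, or 80 × 165 = EUR 13,200. The high end charges the full purchase price, which overstates the cost of a loan lasting the study period.
- Non-alarm video consultations: 0 to 3 per patient, 15 to 30 minutes each, EUR 50 to 100 per hour. Low end: EUR 0. High end: 3 × 0.5 × 100 = EUR 150 per patient, or 150 × 165 = EUR 24,750.
- Routine dashboard review: no figure is assumed. The dashboard log would supply the hours.

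Two pairs of statements also disagree. The monitor and scale are provided at inclusion without restriction in one section, and costed for selected patients in another. Smartphone ownership is an inclusion criterion in Table 1, yet the Smartphone intervention section allows a loan to patients without one. The second pair decides whether the phone cost can arise at all.

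**The case against.** The best case for the protocol is that most of the intervention is already costed and the rest is exceptional. Much of this stands. A reader might infer that devices are under-costed because the list speaks of selected patients. It does not follow: every device provided is costed, and the selected patients can be those who do not use their own equipment. Only the wording differs between sections. A reader might also infer that installation and calls to patients who stop using the app go unpriced. They do not: installation takes place at inclusion, and non-use is itself an alarm.

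On smartphones, the protocol says only that one can be provided. Ownership is an inclusion criterion, so the number lent may be zero. That limits the size, but a supplied phone still has no cost line.

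On video consultations, the reply is that non-alarm ones could enter as care utilisation, and that Table 3 lists healthcare resource use and health expenditure under implementation cost. This is possible and cannot be excluded. It is not secure, because hospital costs come from billing and the Discussion says Belgium has no reimbursement framework for heart failure telemonitoring. A remote contact may therefore produce no bill; that is an inference, not a statement in the protocol. Dashboard review without any contact is harder still to place under care utilisation.

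Detailed costing could also sit in an analysis plan that is not shown. The point here is narrower: the protocol itself states a list that reads as complete, and that list is too short.

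**Conclusion.** The point holds in a limited form. As worded, the costing rule omits supplied or replaced smartphones and caregiver time outside inclusion and alarms. To the extent that these occur and are not captured as care utilisation, the intervention cost and the ICER numerator are understated, and the bias runs in one direction only. The size cannot be established from the protocol. It may be small, and it is zero if no phone is supplied and no non-alarm time goes unpriced. The illustrative euro ranges rest wholly on assumed prices, shares and hours and should not be cited as estimates. A reader might go further and conclude that the app's cost is certainly too low. The document does not support that, because it does not show that any of these inputs will occur in quantity. This is a minor point, worth correcting because the correction is cheap.

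**What to change.** In Health economic analysis, replace the list with a rule that covers:

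- all equipment actually supplied or replaced, with smartphones charged as use over the loan period plus any loss or damage;
- all caregiver time logged in the dashboard, including review without an alarm and video consultations;
- a statement that contacts already billed as care utilisation are not counted again.

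Reconcile the device wording in Digital support platform with that in Health economic analysis. Reconcile the smartphone criterion in Table 1 with the loan in Smartphone intervention.

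The time data are already collected, so the only addition is a count of phones supplied or replaced. The downside is a slightly higher stated intervention cost.

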Interventions because of the trial

Personalised alarm cut-offs can be programmed by the caregiver team. There is no scheduled study contact on top of the usual care contacts. In case of application alarms being triggered, the patient will be called and the situation will be assessed. If needed, the problem will be discussed with a cardiologist. In emergency situations, the patient will be asked to present to the emergency department.

Monitoring of alarms will not be continuous and will only take place during working hours throughout the working week (Monday to Friday) and patients will be instructed to call their general practitioner, the hospital, or the emergency number in case of problems and not to wait until they are contacted.

End-of-trial assessment

At the end of the trial, the assessments listed in Table 2 will be performed. Cost-related data will be collected: healthcare resource use, hospitalisation time, tests, procedures, and health expenditure. Cost-effectiveness will be calculated using healthcare cost data and work productivity and impairment (WPAI) questionnaire to calculate incremental cost-effectiveness ratio (ICER).

Re-evaluation at 12 months

After the end of the inclusion at 6 months, a re-evaluation of outcome parameters will take place at month 12 to evaluate the continued effect of the intervention after cessation.

	Baseline	Final visit month 6
Informed consent and patient information	X	
Medical history: past medical history, symptom control, NYHA classification, smoking behaviour, current medication	X	X
Physical examination including weight, height, blood pressure, heart rate	X	X
Length of initial hospital stay	X	
Registration of medication	X	X
Echocardiography	X	X
12-lead ECG	X	X
Laboratory tests: haemoglobin, haematocrit, leukocytes, thrombocytes, sodium, potassium, creatinine, NT-proBNP	X	X
ePROs: KCCQ-12, EQ5D, HeartQoL, PHQ9, HLS-EU-Q16, EHFSB-9, SUTAQ, WPAI.	X	X
Registration of events: hospitalisation (with the length of stay), emergency department visit, death		X
Cost-evaluation		X

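### Leaving scheduled cardiologist and GP visits out of the costs may bias the saving, because the app can move care into that uncounted category

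*Protocol*

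**What the plan says.** The Health economic analysis section of the Protocol draws the cost boundary.

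- **Left out:** "Scheduled hospitalisations for elective procedures", and also "scheduled visits with the cardiologist or general practitioner will not be included in the cost-evaluation".
- **Counted for the intervention:** app data management, supplied devices, and "personnel costs for inclusion and time spent on follow-up of alarms".
- **Classification:** "A distinction will be made between scheduled and non-scheduled hospitalisations". The section does not say into which class a visit or admission prompted by an alarm would fall.
- **Estimand:** incremental cost is the difference in mean total cost per patient between the app group and either the 2019 historical cohort or the patients who refuse participation.

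The section headed Interventions because of the trial describes what an alarm sets in motion. The patient is telephoned and the position judged. The next step is conditional: "If needed, the problem will be discussed with a cardiologist". For the most urgent cases the rule is: "In emergency situations, the patient will be asked to present to the emergency department". The Digital support platform section adds that caregivers can start a video consultation after looking at the patient's data. Data collection during the trial says that the dashboard logs therapy changes and contacts.

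**The concern.** The app is meant to catch deterioration early. One natural result of catching it early is a booked cardiology visit in place of an unplanned admission. Under the stated boundary the admission that did not happen lowers the app group's cost, while the visit that took its place adds nothing.

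Leaving out a cost category does no harm when that category is the same in all groups. Here it is one that the intervention itself can change. The 2019 cohort was treated before the trial's alarms existed, and the refusal group does not use the app, so there is no reason to expect the omission to cancel. A boundary without scheduled outpatient care also sits badly with a definition of incremental cost as a difference in total cost.

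Cost-effectiveness is a stated objective, and the Discussion links a successful result to reimbursement in Belgium. A saving based on unscheduled care alone is open to the reply that care was merely moved to where it was not counted.

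**Working it through.** The Protocol states no unit cost, visit rate, admission rate or expected saving, so there is no figure of its own to reproduce. The check is an accounting identity followed by an illustration on assumed values.

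**Identity.** Take the cost of one unplanned admission as 1. Let

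- d = unplanned admissions averted per patient,
- m = net change in scheduled outpatient contacts per patient, app group minus comparator,
- c = cost of one such contact relative to one unplanned admission.

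Before the cost of the app itself:

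- counted saving = d
- full saving = d − m·c
- error = counted − full = m·c

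The app's own costs enter both lines equally, so they leave the error unchanged. The error is zero if m = 0, favours the app if m > 0, and works against it if m < 0. The documents give none of d, m or c.

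**Illustration (all values assumed).** Let d be 0.05, 0.10 or 0.20 and c = 0.02. The ratio of counted to full saving is d / (d − 0.02·m).

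| m | d = 0.05 | d = 0.10 | d = 0.20 |
|---|---|---|---|
| −1 | 0.05/0.07 = 0.71 | 0.10/0.12 = 0.83 | 0.20/0.22 = 0.91 |
| 0 | 1.00 | 1.00 | 1.00 |
| +1 | 0.05/0.03 = 1.67 | 0.10/0.08 = 1.25 | 0.20/0.18 = 1.11 |
| +3 | full saving 0.05 − 0.06 = −0.01 (a loss) | 0.10/0.04 = 2.50 | 0.20/0.14 = 1.43 |

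The full saving vanishes when m = d/c, that is at 0.05/0.02 = 2.5, 0.10/0.02 = 5 and 0.20/0.02 = 10 extra visits per patient. A cheap item can therefore matter when few admissions are averted.

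**Can m differ from zero?** The alarm pathway, the cardiologist discussion and the caregiver-started video consultation are all routes by which the app could change outpatient contacts. Nothing in the Protocol says by how much or in which direction.

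**The case against.** A reader might infer that the saving *is* overstated. The documents do not support that. The alarm pathway names a call, a discussion with a cardiologist and, in emergencies, the emergency department; it never mentions a booked visit. The Protocol adds no planned study contacts to usual care, and video consultation could replace visits as well as add them. The sign of m is open.

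Nor are the intervention's consequences left out wholesale. Staff time on alarms is costed, and alarm-driven emergency attendances are not in the excluded class. A visit prompted by an alarm could also be read as unscheduled and therefore counted. These points narrow the gap without closing it: staff time on an alarm is not the cost of the visit that follows, and the class of that visit is left undefined.

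Two further inferences should be resisted. Planned admissions for decompensation are not clearly excluded, since the wording covers admissions for elective procedures; no amount should be attached to them. And End-of-trial assessment ("Cost-related data will be collected: healthcare resource use, hospitalisation time, tests, procedures, and health expenditure") and Table 3 do not contradict the exclusion. They name the kinds of data collected, and analysing a defined part of them is consistent.

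The Protocol also gives a reason for its focus: admissions dominate heart failure costs. That is a fair reason to concentrate on admissions, but it does not show that the omitted visits are equal between groups.

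Finally, a careless remedy could tilt the comparison towards the app. Table 1 bars patients with revascularisation, TAVI, MitraClip or CRT planned within 3 months, while the 2019 cohort is described as every heart failure admission to cardiology. Counting planned procedures would load them onto 2019. The introduction also notes that the pandemic made it hard for patients to see their cardiologist, so fewer visits than in 2019 need not be due to the app. Both points stand and shape the fix.

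**Conclusion.** The point holds for outpatient care. The Protocol fixes a cost boundary that drops a category the app can alter, while defining incremental cost as a difference in totals. The resulting error is m·c: the saving may be overstated, and the ICER too favourable, if scheduled contacts rise under the app; the reverse applies if they fall. Its size cannot be derived from the documents. The illustrative ratios rest entirely on assumed values (0.05 to 0.20 admissions averted, a visit at 2% of an admission) and show only that the effect could range from none to material. The direction that favours the app is plausible, given how the app is meant to work, but it is not shown. The exclusion of elective-procedure admissions is defensible as long as the 2019 cohort is not restricted in the way Table 1 restricts the app group.

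**What to change.** - **Base case:** count hospital-billed outpatient cardiology contacts, scheduled or not, in the app group, the 2019 cohort and the refusal group. A visit or admission set off by an alarm counts even when booked in advance, elective procedures apart.
- **Sensitivity analysis:** report the present unscheduled-only definition alongside.
- **Elective-procedure admissions:** keep them out of every group unless the Table 1 exclusion of procedures planned within 3 months is first applied to the 2019 cohort.
- **GP visits:** leave them out if no group's billing source holds them, and say so.
- **Interpretation:** state that pandemic-related changes in visits limit the comparison with 2019.
- **Wording:** bring the exclusion and the definition of incremental cost into line.

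Cost: a few more lines to extract from hospital bills that the Protocol already plans to collect, and a saving that may turn out less favourable.
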